#### Table 5: Threshold numbers for stopping the study

Number of subjects in the experiment	Stop if the number of subjects who have developed any of the specified TRSAE's reaches:	
25	9	

We investigated the performance of the above stopping rule by a simulation study. In each simulation run, we generated a study with 25 independent Bernoulli trials, each had a probability p for having TRSAE and q=1-p for not having TRSAE and compared the TRSAE outcomes with the above stopping boundary to determine whether the study was stopped. We repeated the simulation 100,000 times and computed the proportion of stopped studies (*i.e.* "number of stopped studies"/100,000) which were stopped using the above stopping rule. Table 6 summarizes the proportion of stopped studies under a number of scenarios for p:

Table 6: Predicted rates of stopping under various scenarios

Probability of TRSAE = p	0.10	0.15	0.20	0.25	0.30	0.35	0.40	0.45
Proportion of stopped studies	1.8%	7%	18.2%	35.7%	55.5%	73.2%	86.4%	94.1%
Average number of subjects	24.7	23.9	22.4	20.1	17.3	14.5	11.8	9.7
Average number TRSAEs	2.5	3.6	4.5	5	5.2	5.1	4.7	4.3

These simulation results suggest that our stopping rule has a low probability stopping a study when the proportion of TRSAE within the 24-week is below 20%, and the probability of stopping a study is high when the true proportion of TRSAE within the 24-week exceeds 20%. Therefore, we believe that our Bayesian stopping rule for TRSAE has satisfactory statistical properties.

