## 8.5. Stopping rules

The study will be monitored to ensure that the occurrence of a specified set of treatment related serious adverse events (TRSAEs) that occur during the treatment period does not substantially exceed an anticipated rate. The following specified TRSAEs determined to be probably or definitely related to EPAG will be considered for early stopping of the study:

- 1. Death considered to be probably or definitely related to eltrombopag
- 2. Any Grade IV toxicity excluding readily reversible metabolic or laboratory abnormalities
- 3. Grade IV thrombosis/embolism

We anticipate the rate of these specified TRSAEs within the 24-week study period to be 20% or less. Following Geller *et al.* (90), our stopping rule is determined by a Bayesian approach. The stopping boundary for an experiment is reached if the Bayesian posterior probability that the true probability of developing one or more of the specified TRSAE's exceeds this benchmark rate of 20% is at least 90%. We take our prior distribution to be a beta distribution with parameters ( $\alpha$ ,  $\beta$ ) = (1, 4). The parameters are chosen so that the mean  $\alpha / (\alpha + \beta) = 0.2$  as the expected proportion of specified TRSAE's and the sum  $\alpha + \beta = 5$  as the "worth" we place on our prior clinical opinion. This indicates that the relative weight we place on our prior opinion is 5/25=20% of the weight we will place on the results of the new study. Hence when we make decisions about stopping the study, the data from the study will dominate over the prior opinion. All participants will be included in monitoring and evaluation for safety. Table 5 summarizes the threshold numbers for stopping the study.

Number of subjects in the experiment	Stop if the number of subjects who have developed any of the specified TRSAE's reaches:
≤ 5	3
≤ 9	4
≤ 12	5
≤ 16	6
≤ 20	7
≤ 24	8

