# 9.2.3. Serious Adverse Events Management

Serious adverse events will be attributed as definitely (clearly related to the research), probably (likely related to the research), possibly (may be related to the research), unlikely

(doubtfully related to the research) and unrelated (clearly not related to the research) (Table 8).

Treatment related SAEs (TRSAEs) are those attributed as definitely, probably, or possibly related (Table 8) that will be monitored and considered for early stopping of the study according to statistically determined criteria. These include death and any grade IV toxicity considered to be probably or definitely related to study medication.

Hospitalizations for administrative issues (to receive a transfusion) or upgrading to ICU for routine monitoring will not be considered as SAE.

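### Section 8.5 says the safety rule is likely to stop the trial once the event rate exceeds 20%, but its own Table 6 gives 35.7% at 25% and 55.5% at 30%; Table 5 and the counted events also need reconciling

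*Combined protocol and SAP*

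**What the plan says.** Section 8.5 sets a benchmark of 20% for the proportion of subjects with a specified TRSAE over 24 weeks. The study is to stop when the posterior probability that the true rate "exceeds this benchmark rate of 20% is at least 90" per cent. On the prior it says: "We take our prior distribution to be a beta distribution with parameters" (1, 4).

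Table 5 turns this into counts, headed "Stop if the number of subjects who have developed any of the specified TRSAE's reaches": 3 for up to 5 subjects, 4 up to 9, 5 up to 12, 6 up to 16, 7 up to 20, 8 up to 24, and 9 at 25. Table 6 reports the simulated behaviour of that boundary, and the text below it concludes that "the probability of stopping a study is high when the true proportion of TRSAE within the 24-week exceeds 20" per cent, and on that basis calls the rule's properties satisfactory.

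On which events count, 8.5 states: "The following specified TRSAEs determined to be probably or definitely related to EPAG will be considered for early stopping of the study". Its list includes "Any Grade IV toxicity excluding readily reversible metabolic or laboratory abnormalities". Section 9.2.3 says: "Treatment related SAEs (TRSAEs) are those attributed as definitely, probably, or possibly related (Table 8) that will be monitored and considered for early stopping". It continues: "These include death and any grade IV toxicity considered to be probably or definitely related to study medication".

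**The concern.** The closing claim in 8.5 describes a rule that becomes likely to stop the trial as soon as the true rate passes 20%. The figures above it describe a rule that more often than not lets the trial run to completion at 25%, and is little better than even at 30%. This is the only formal safety boundary in a single-arm trial that enrols children from age 2. A board or ethics committee relying on the sentence would think the trial better protected against a moderate excess of toxicity than it is.

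The other two points concern how the rule is applied. If the first two subjects both have an event, the written criterion says stop and Table 5 says continue. If a grade IV laboratory value reverses quickly, or an event is judged possibly related, 8.5 and 9.2.3 can give different counts against the same boundary.

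**Working it through.** **Inputs.** All from 8.5: benchmark 0.20; posterior threshold 0.90; prior Beta(1, 4); Table 5 boundary; 25 independent Bernoulli subjects with the boundary checked after each one.

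**Step 1: reproduce Table 6.** Let f(n, x) be the probability of reaching n subjects with x events without having stopped. Then f(n, x) = f(n−1, x)(1−p) + f(n−1, x−1)p. After each subject, the probability at or above the Table 5 count is moved to the stopped total.

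| True rate p | Table 6, stopped | Exact, Table 5 | Exact, 2 of 2 added | Difference (points) |
|---|---|---|---|---|
| 0.10 | 1.8% | 1.71% | 2.38% | 0.7 |
| 0.15 | 7% | 7.02% | 8.16% | 1.1 |
| 0.20 | 18.2% | 18.42% | 19.79% | 1.4 |
| 0.25 | 35.7% | 35.71% | 37.01% | 1.3 |
| 0.30 | 55.5% | 55.50% | 56.51% | 1.0 |
| 0.35 | 73.2% | 73.35% | 74.00% | 0.7 |
| 0.40 | 86.4% | 86.36% | 86.71% | 0.3 |
| 0.45 | 94.1% | 94.11% | 94.27% | 0.2 |

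Table 6 agrees with the exact values to about 0.2 points, and its average numbers of subjects and events also reproduce. It was evidently simulated from Table 5 as printed.

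**Step 2: compare the sentence with the table.** At p = 0.25 the study is not stopped with probability 100 − 35.7 = 64.3%. At p = 0.30, one and a half times the benchmark, it is not stopped with probability 44.5%. Solving the same recursion for p gives 50% stopping at 0.286, 80% at 0.373 and 90% at 0.420.

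**Step 3: re-derive Table 5.** After x events in n subjects the posterior is Beta(1 + x, 4 + n − x). The probability that p exceeds 0.20 equals P(Bin(n + 4, 0.2) ≤ x).

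- n = 1, x = 1: 0.737, so no boundary is possible.
- n = 2, x = 2: P(Bin(6, 0.2) ≤ 2) = 0.8⁶ + 6(0.2)(0.8⁵) + 15(0.2²)(0.8⁴) = 0.2621 + 0.3932 + 0.2458 = 0.9011. The criterion is met, but Table 5 asks for 3.
- n = 3, 4, 5 with x = 3: 0.9667, 0.9437, 0.9144, all matching Table 5.
- n = 9, x = 4: 0.9009, matching Table 5.
- For every n from 3 to 25, the smallest x reaching 0.90 equals the Table 5 entry.

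The mismatch is confined to n = 2. A stricter cut-off does not explain it, because Table 5 accepts 4 of 9 at 0.9009, which is closer to 0.90. Section 8.5 states no minimum number of subjects.

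**Step 4: set the event definitions side by side.**

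| | 8.5 | 9.2.3, first sentence | 9.2.3, second sentence |
|---|---|---|---|
| Attribution | probably, definitely | possibly, probably, definitely | probably, definitely |
| Quickly reversible laboratory or metabolic grade IV findings | excluded | not addressed | not excluded |

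Section 9.2.3 therefore differs from 8.5 on the exclusion, and its first sentence differs on attribution from both its second sentence and 8.5.

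**The case against.** The strongest reply is that nothing was computed wrongly and little follows from the wording. Section 8.5 opens by aiming to detect a rate that substantially exceeds the anticipated one, and for a substantial excess the rule does well: 73.2%, 86.4% and 94.1% at 35%, 40% and 45%. The plan sets no target stopping probability, so the 50% and 80% marks are imposed from outside. The true figures sit directly above the sentence. That limits the harm, but the sentence drops the qualifier, and no ordinary meaning of a high probability covers 36%.

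On Table 5, the criterion is passed by 0.0011 at one sample size, and Tables 5 and 6 agree with each other. The situation would also be rare. With 25 subjects accrued over 2.5 to 3 years (section 8.3), and assuming even accrual, about 4 to 5 enter in any 24 weeks, so two events with only two subjects enrolled is unlikely. All of this stands and makes the point minor, but the written criterion and the table still disagree.

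On the event definitions, 9.2.3 can be read as naming a broad class and then the subset that counts. Its reference to statistical criteria leads back to 8.5, and section 8.6 also excludes reversible laboratory findings when taking a subject off study. That reading is reasonable, but the first sentence itself ties early stopping to possibly related events, and the second does not present itself as a restriction.

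The board's power to recommend termination (9.1) and expedited reporting of unexpected related serious events (9.2.4.2) provide a backstop.

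**Conclusion.** The concern holds on all three counts and should be corrected.

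- **Main point.** The claim that stopping is likely once the rate exceeds 20% is not a property of this rule. Stopping is 35.7% at 25% and 55.5% at 30%, and reaches 80% only near 37%. The error is in the interpretation, not in Table 6.
- **Table 5.** It departs from the stated criterion at two events in two subjects and nowhere else. The effect on overall stopping is at most 1.4 points.
- **Counted events.** Sections 8.5 and 9.2.3 are inconsistent on possibly related events and on reversible laboratory findings. The size of this effect cannot be calculated, because the documents do not say how often such events are expected.

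The figures assume what the plan's own simulation assumes: independent subjects, a constant event probability, and the boundary checked after each subject with outcomes known at once. The findings do not show that the boundary itself is unsuitable. Whether 36% to 56% stopping at true rates of 25% to 30% is acceptable is a judgement for the sponsor and the board, to be made on the correct figures.

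**What to change.** 1. In 8.5, replace the concluding sentence with the figures. For example: the rule stops 36% of studies at a true rate of 25%, 56% at 30%, 73% at 35% and 86% at 40%; stopping exceeds 50% only above about 29% and 80% only above about 37%. Rest the judgement that the rule is adequate on those numbers.
2. Make the criterion and Table 5 agree. Either add the boundary of 2 events in 2 subjects and rerun Table 6 (the last two columns of the table in step 1 show the stopping probabilities to expect), or state that the boundary applies from the third subject, in which case Table 6 stands.
3. Reconcile 8.5 with both sentences of 9.2.3, so that one list of events, one attribution level and one statement of the laboratory exclusion apply. A cross-reference from 9.2.3 to a single definition would be enough. Which events count is for the sponsor to decide.

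The cost is wording edits in two sections, plus one clarifying sentence or one table row with a rerun of the simulation. Sample size and the primary analysis do not change.

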# 8.6. Off study criteria

*Per subject choice:* Subjects may withdraw from study at their request. The risks of withdrawing will be discussed, as will alternative treatment options. Those subjects who choose to withdraw while taking eltrombopag will be strongly encouraged to continue to have labs monitored until he/she initiates alternative therapy.

**Per principal investigator decision:** Should any of the following events occur during the study period, or in the extension treatment arm in responders, EPAG will be discontinued. The subject will be followed until resolution of the event. For study purposes labs relevant to the adverse event will be monitored for 30 days after discontinuation of EPAG. We will offer patients a follow-up evaluation at the NIH 6 months following being taken off EPAG treatment either due to lack of response or because they met other criteria for coming off study, but this visit will not be required. If they do not return to the NIH, we will contact their primary hematologist for information on their current hematologic status 6 months following their final dose of eltrombopag, and then take

them off study. If a patient initiates an alternative disease directed therapy at any time, the subject's participation on this study will be considered complete and the subject will go off study.

- Intolerance of EPAG not resolved by dose reduction
- Life threatening acute hypersensitivity reaction
- Thrombosis/embolism (DVT, PE, stroke or TIA, myocardial infarction) other than central line thrombosis
- Persistent hepatotoxicity as defined in §10.3.1
- New or worsening morphological abnormalities or cytopenia(s) indicative for transformation to MDS or AML
- No treatment response by week 24 (+/- 7 days)
- Any Grade IV toxicity considered related to the study medication excluding readily reversible metabolic or laboratory abnormalities or hematologic toxicities (see §9.2.1, 10.3.1)
- Significant progression of disease such as development of a solid tumor while on EPAG, or a concomitant condition that would make the subject ineligible for further protocol participation
- Pregnancy or unwillingness to use acceptable forms of contraception
- Initiation of non-protocol therapy for Diamond-Blackfan anemia
- Subject non-compliance
- Lost to follow-up
  - Multiple, good-faith efforts will be made according to good standards of clinical research to re-establish contact with any subjects prior to declaring them lost to follow-up and removed from study
- Study completion

*Completion of protocol participation:* Three years after a responding patient agrees to continue the drug on the extension phase, protocol participation will be deemed complete. During the initial consenting process, the patient will be informed that eltrombopag cannot be provided after study completion. For responding patients wishing to continue eltrombopag, we will assist the referring physician with helping the patient obtain eltromobopag, including via the Novartis Patient Assistance Program. Once off study, subjects will be referred back to the referring physician or consented to the Hematology Branch evaluation and treatment protocol (94-H-0010) or evaluated for eligibility for another Branch protocol, depending on the wishes of the subject and availability of appropriate additional clinical trials at the NIH.

Death: Death of subject

# 9. Data and Safety Monitoring

# 9.1. Safety Monitoring

**Principal Investigator:** Accrual, efficacy and safety data will be monitored by the Principal Investigator, [name]., Ph.D.

**NIH Intramural IRB:** Prior to implementation of this study, the protocol and the proposed patient consent and assent forms will be reviewed and approved by the properly constituted Institutional Review Board (IRB) operating according to Title 45 CFR 46. This committee will also approve all amendments to the protocol or informed consent, and conduct continuing annual review so long as the protocol is open to accrual or follow up of subjects.

**NHLBI Hematology DSMB:** The NHLBI Hematology Data Safety and Monitoring Board (DSMB) will review the protocol at 6- to 12-month intervals, and the interval will be determined by DSMB. A progress report will be forwarded to the DSMB at these times and their recommendations will be expeditiously implemented. The DSMB may recommend early termination of the study for considerations of safety and efficacy.

**Monitoring:** As per ICH-GCP 5.18 and 21 CFR 312.50, clinical protocols are required to be adequately monitored by the study sponsor. The monitoring of this study will be conducted by an independent contract organization working under an agreement with NHLBI to monitor aspects of the study in accordance with the appropriate regulations and the approved protocol. The objectives of a monitoring visit will be:

- 1) to verify the existence of signed informed consent form (ICF) and documentation of the ICF process for each monitored subject;
- 2) to verify the prompt and accurate recording of all monitored data points, and prompt reporting of all SAEs;
- 3) to compare abstracted information with individual subjects' records and source documents (subject's charts, laboratory analyses and test results, physicians' progress notes, nurses' notes, and any other relevant original subject information);
- 4) to help ensure investigators are in compliance with the protocol.

The monitors also will inspect the clinical site regulatory files to ensure that regulatory requirements (Office for Human Research Protections-OHRP) and applicable guidelines (ICH-GCP) are being followed. During the monitoring visits, the investigator (and/or designee) and other study personnel will be available to discuss the study progress and monitoring visit.

9.2. Event Characterization and Reporting

Events include *adverse events* (AE), *serious adverse events* (SAE), *protocol deviations* (PD), *unanticipated problems* (UP), and *non-compliance*.

The principal investigator will review all events (AEs, SAEs, PDs, UPs and non-compliance) to determine the seriousness, expectedness, and reportability of the event. As required and/or needed, the principal investigator will review the events with the Sponsor to make the final determination of seriousness and reportability.

9.2.1. Definitions

Please refer to Policy 801 "Reportable Research Events" for current definitions.

9.2.2. Adverse events Management

AEs will be graded by severity utilizing CTCAE version 5.0 (summarized in Table 7) and attributed (unrelated, unlikely, possibly, probably or definitely) to study medication and/or disease (Table 8). The current CTCAE grading criteria can be downloaded from the CTEP homepage at:

https://ctep.cancer.gov/protocolDevelopment/electronic\_applications/ctc.htm.

Grade	Category	Description
1	Mild	Mild; asymptomatic; clinical or diagnostic observations only; intervention not indicated
2	Moderate	Moderate; minimal, local or noninvasive intervention indicated; limiting age-appropriate instrumental ADL 
3	Severe	Severe or medically significant but not immediately life-threatening; hospitalization or prolongation of hospitalization indicated; disabling; limiting self-care ADL 
4	Life threatening	Life-threatening consequences; urgent intervention indicated
5	Death	Death related to AE
1-		

#### Table 7: Grading of adverse events

Instrumental ADL refers to preparing meals, shopping for groceries or clothes, using the telephone, managing money, etc.

**Self-care ADL** refers to bathing, dressing and undressing, feeding self, using the toilet, taking medications, and not bedridden.

#### Table 8: Attribution of adverse events

Relationship	Attribution	Description
Unrelated to investigational	Unrelated	The AE is clearly NOT related to the intervention
agent/intervention 	Unlikely	The AE is doubtfully related to the intervention
Related to investigational agent/intervention 	Possibly	The AE may be related to the intervention
	Probably	The AE is likely related to the intervention
	Definitely	The AE is clearly related to the intervention

**NOTE:** AEs listed as 'possibly, probably, or definitely' related to the investigational agent/intervention are considered to have a suspected 'reasonable causal relationship' to the investigational agent/intervention (ICH E2A).

In view of the underlying disease (Diamond-Blackfan anemia), all patients will enter the study with abnormally low blood counts that would meet criteria for grade 2 and more commonly higher toxicity. Also, platelet and red blood cell counts will be impacted by frequent transfusions. Therefore, AEs regarding low hematologic lab values, including thrombocytopenia or platelet-transfusion dependence, anemia or red cell transfusion dependence, neutropenia, lymphopenia, or leukopenia are not evaluable and will not be recorded.

Non-hematologic abnormal laboratory findings used to evaluate the safety of this protocol regimen will include any change from laboratory assessments done prior to first dose of study medication that result in a progression to grade 3 or 4 laboratory toxicity or are characterized by any of the following:

- Results in discontinuation from the study
- Is associated with clinical signs or symptoms
- Requires treatment or any other therapeutic intervention
- Is associated with death or another serious adverse event, including hospitalization
- Is judged by the Investigator to be of significant clinical impact
- If any abnormal laboratory result is considered clinically significant, the investigator will provide details about the action taken with respect to the test drug and about the patient's outcome.

Adverse Events that meet the criteria of CTCAE v 5.0 grade 2 and above plus laboratory abnormalities that meet the definition of an AE will be captured at each study visit on the appropriate case report form (CRF) regardless of relationship. AEs and SAEs whether volunteered by the patient, discovered by study personnel during questioning, or detected through physical examination, clinically significant laboratory test, or other means will be recorded. Information to be collected includes event description, time of onset, clinician's assessment of severity, relationship to study drug and study procedure (assessed only by those with the training and authority to make a diagnosis), and time of resolution/stabilization of the event. These AEs will be followed to adequate resolution.

Abnormal non-hematologic laboratory values recorded in the database will be recorded at the highest grade and resolved in the database when the value is a grade 2 or lower. However, with the exception of ALT, AST and direct bilirubin any laboratory abnormalities higher than grade 2 will automatically result in discontinuation of the study drug.

Hypertension CTCAE v5 Grade 1 is not an applicable category for this study and therefore only hypertension greater than grade 2, that require medical intervention, will be documented.

Unscheduled laboratory results or patient reports that have been sent in addition to the protocol required ones will be reviewed for AEs and will be recorded on secure network drives or in approved alternative sites that comply with NIH information security standards and not in the research database.

Thirty days after the last dose of study drug, adverse event collecting and reporting will be limited to serious adverse events considered possibly, probably, or definitely related to study drug.

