Biopsy has historically been used to measure the liver iron concentration (LIC), and as such has served as a measure of total body iron concentration. It is generally considered the "gold standard" for assessing iron load and is more accurate and reliable than serum ferritin (20-22). However, this highly invasive technique, which carries significant risks of complication, is subject to considerable sampling error and bias, and is somewhat limited in the number of times it can be performed (23, 24). Consequently, it has fallen out of favor, especially for routine monitoring of iron loading in asymptomatic patients. For these reasons, annual surveillance with magnetic resonance imaging (MRI) has become the standard of care, especially for any patients on or transitioning to chronic transfusion therapy. The presence of iron alters the signal characteristics of effective T2 (T2\*) sequences, where iron concentration leads to an inversely proportional shortening of relaxation. This shortening can be compared to established standards and from this,

LIC can be inferred. This technique has proven to be reliable, reproducible, and correlates well with traditional biopsy results (25, 26). The sequences can be obtained quickly, do not require contrast, and can even include measurements of cardiac and pancreatic iron. Thus, with increasing access to MRI, have replaced biopsy in most clinical settings, even in relatively resource-poor settings (27-29). It also has proven to be a useful tool in the research setting, monitoring the impacts of various treatments upon iron loading (30, 31).

Chelation therapy has proven revolutionary in the management of transfusion-dependent anemias including DBA, greatly reducing morbidity from the disease. Oral chelation agents (deferiprone and deferasirox) have also proven efficacious, while improving quality of life through ease of administration. However, in addition to the difficulties of adding yet another layer to the management of the disease, these agents also carry risks themselves. The most clinically significant complication is the potentially fatal agranulocytosis associated with deferiprone reported in several DBA cases and leading to an FDA black-box label (32, 33). Nonetheless, all of the chelation agents carry risks including sensorineural hearing loss and retinopathy, requiring additional clinical vigilance.

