## 5.5.2. Peripheral blood smear shows new morphological abnormalities

The presence of persistent morphologic abnormalities (red cell teardrop forms or immature blasts) or the development of significant sudden worsening of platelet or neutrophil counts while on study will require discontinuation of EPAG and performance of a bone marrow examination to assess for development of abnormal fibrosis or progression to MDS or AML.

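### Section 9.2.2 bars recording of low platelet and white cell adverse events on a premise the documents establish only for red cells, and its wording conflicts with the stopping-rule events in 8.5 and 9.2.3

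*Combined protocol and SAP*

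**What the plan says.** Section 9.2.2, in the text below Table 8, removes "AEs regarding low hematologic lab values" from adverse event recording in every lineage. It names low platelets or platelet transfusion dependence and anemia or red cell transfusion dependence, and then says "neutropenia, lymphopenia, or leukopenia are not evaluable and will not be recorded". It makes no exception for grade, change from baseline, relatedness or seriousness. High-count events such as thrombocytosis are not affected.

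Two reasons are given. The first is that "all patients will enter the study with abnormally low blood counts that would meet criteria for grade 2 and more commonly higher toxicity". The second is that "platelet and red blood cell counts will be impacted by frequent transfusions".

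For non-hematologic laboratory values the same section uses a different standard. It includes changes from the pre-dose assessment "that result in a progression to grade 3 or 4 laboratory toxicity", along with several clinical triggers. It also has events attributed "to study medication and/or disease".

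Section 8.2.1 makes the CTCAE toxicity profile at 6 months the primary safety endpoint. Section 8.5 counts toward Table 5 the specified treatment-related serious adverse events that are probably or definitely related to eltrombopag. These include Grade IV toxicity, except readily reversible metabolic or laboratory abnormalities. Section 9.2.3 describes the same monitored events without that exception. Neither section excludes hematologic toxicity.

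**The concern.** A rule that low counts cannot be evaluated makes sense for a lineage that is abnormal in everyone at entry and is being transfused. Here that lineage is red cells. Extending the rule to the other lineages means that a subject who enters with normal neutrophils and becomes severely neutropenic on eltrombopag generates no graded, attributed entry in the primary safety profile. An empty row would reflect the recording rule and could be mistaken for evidence of safety.

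This matters in this population. Section 5.7 lets deferiprone already in use continue on study, and section 2.2 describes "potentially fatal agranulocytosis associated with deferiprone reported in several DBA cases". A new neutropenia on both drugs is the kind of event a safety profile should show and discuss.

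The stopping rule raises a second question. If the same event is serious, related, Grade IV and not readily reversible, two readers could reach different Table 5 counts, depending on whether they follow 8.5 and 9.2.3 or 9.2.2.

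**Working it through.** **Step 1. Is the premise established, lineage by lineage?**

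| Lineage | Low at entry in all subjects? | Transfusion reason applies? |
|---|---|---|
| Red cells | Supported: 4.1.2 requires hemoglobin below 9.0 g/dL or a minimum red cell transfusion load | Yes |
| Platelets | Not established: the only criterion (4.2.1) is an upper limit of 400,000/µL | Stated, but nothing shows that entrants receive platelet transfusions |
| Neutrophils, lymphocytes, white cells | Not established: no entry criterion | No: the sentence names platelets and red cells only |

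The diagnostic tetrad in 2.2 describes anemia without other significant cytopenias. Sections 2.1 and 2.2 say that defects in other lineages can emerge with time, and reference 7 reports a trilineage defect in refractory disease. Abnormal baselines are therefore plausible in some entrants. Section 2.2 presents later cytopenias as a possibility, not as something found in every patient.

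**Step 2. Does the rest of the protocol treat these counts as not evaluable?** No. Section 5.5.2 requires action on "significant sudden worsening of platelet or neutrophil counts while on study". Section 8.6 lists new or worsening cytopenias that point to MDS or AML. Both assume that change on study can be detected.

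**Step 3. What is kept, and what is lost?**
- Kept: blood counts every 2 weeks, with all laboratory data recorded (6.3).
- Kept: a secondary endpoint on platelet and neutrophil counts (8.2.2), though it omits lymphocytes and total white cells and specifies no grading or attribution.
- Kept: clinical consequences such as infection or bleeding, as adverse events at grade 2 and above (9.2.2).
- Kept: serious cases, through 9.2.2, 9.2.3, 9.2.4.2 and 9.3.
- Lost: a CTCAE grade, an attribution and a place in the primary safety profile for low-count events.

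**Step 4. What could the profile say if these events were recorded?** With 0 events in n subjects, the exact two-sided 95% upper limit is 1 − 0.025^(1/n).
- n = 25: 13.7%
- n = 20: 16.8%
- n = 15: 21.8%

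The values 20 and 15 are assumptions, allowing for subjects already at grade 4 before dosing. The documents give no such number. A laboratory-only limit could be computed from the recorded counts, but the plan does not specify one and it would carry no attribution.

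**Step 5. The stopping rule as planned.** The rule stops when P(p > 0.20) is at least 0.90 under a Beta(1 + x, 4 + n − x) posterior. This reproduces the Table 5 thresholds for n = 3 to 25. At n = 2, two events already give 0.901, while the first row asks for three; this has no bearing here.

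For Table 6, I carried the probability of x events among studies not yet stopped from subject 1 to 25: P_n(x) = (1 − p)·P_{n−1}(x) + p·P_{n−1}(x − 1). At each n, the mass at or above the Table 5 threshold was removed as stopped.

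| p | 0.10 | 0.15 | 0.20 | 0.25 | 0.30 | 0.35 | 0.40 | 0.45 |
|---|---|---|---|---|---|---|---|---|
| Table 6 | 1.8% | 7% | 18.2% | 35.7% | 55.5% | 73.2% | 86.4% | 94.1% |
| Exact | 1.7% | 7.0% | 18.4% | 35.7% | 55.5% | 73.4% | 86.4% | 94.1% |

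The planned figures are sound.

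**Step 6. What the ambiguity could do.** At 16 subjects the threshold is 6. With five other qualifying subjects, the posterior probability is 0.804 and the trial continues. If one qualifying cytopenia in a sixth subject is counted, it is 0.913 and the boundary is reached.

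In rates, suppose related Grade IV cytopenias add to the share of subjects with any qualifying event. The added rates are assumptions.

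| Other events | No addition | +2 points (exact) | +5 points (Table 6) | +10 points (Table 6) |
|---|---|---|---|---|
| 10% | 1.8% (exact 1.7%) | 3.2% | 7% | 18.2% |
| 15% | 7% | – | 18.2% | 35.7% |
| 20% | 18.2% (exact 18.4%) | 24.8% | 35.7% | 55.5% |

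**The case against.** The best defence has four parts.

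First, the trial enrolls relapsed, refractory or steroid-intolerant patients aged 2 or older, not infants at presentation, and the protocol itself describes progressive cytopenias in such patients (2.1, 2.2, 2.5). This stands in part. It makes abnormal baselines credible for some subjects, but not for all, and a comparison with each subject's own baseline deals with it directly.

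Second, surveillance is stronger than the recording rule suggests, for the reasons in Step 3. This stands. A reader might infer that cytopenias will go unseen or unmanaged, or that the count data are lost. The documents do not support that.

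Third, a Table 5 event must be serious, Grade IV, probably or definitely related and, under 8.5, not readily reversible. Serious events have attributed routes: 9.2.2 says serious events are recorded, 9.2.3 requires attribution, and 9.3 requires every serious event to be reported with its relationship assessed. This also stands. A reader might infer that the stopping rule will miss events, but that is not shown. What remains is a wording conflict, because the bar in 9.2.2 has no exception for serious events. Whether an isolated Grade IV count is serious cannot be settled here, because 9.2.1 refers definitions to an outside policy.

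Fourth, recording would not by itself identify deferiprone as the suspect. The existing fields rate the relation to study drug, study procedure and disease, with no category for a co-medication. This is correct, and the fix has to add that note.

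**Conclusion.** The point holds as a faulty stated rule that should be fixed, not as a fatal flaw. The non-recording rule covers all lineages while its premise is established for one. Followed as written, it leaves the primary safety profile unable to show a graded, attributed, treatment-emergent low platelet, neutrophil, lymphocyte or white cell event.

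The stopping-rule part is narrower. Sections 8.5, 9.2.2 and 9.2.3 disagree on whether a serious, related Grade IV cytopenia is recorded and counted. A reader might also see a contradiction with 8.6, which does exclude hematologic toxicities. It is not one: that exclusion governs individual off-study decisions. It shows only that such an exclusion was written there and not into the stopping rule.

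The size of any effect is unknown. The documents give neither a cytopenia rate nor a number of subjects with low baseline counts outside red cells, so the reduced denominators and added event rates above are illustrations. The conclusion rests on the text and does not depend on them.

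**What to change.** 1. In 9.2.2, limit the non-recording exemption to anemia and red cell transfusion dependence.
2. Record low platelet, neutrophil, lymphocyte and white cell events when they progress from the subject's own pre-dose grade to grade 3 or 4, the standard 9.2.2 already uses for non-hematologic laboratory values. Keep the existing rating of relationship to study drug, and add a note of any suspected co-medication and of recent platelet transfusion.
3. In the 6-month safety report, add a table of shifts from baseline by lineage, with the number evaluable in each.
4. Reconcile 8.5, 9.2.2 and 9.2.3, and state in 8.5 whether a serious, related, not readily reversible Grade IV cytopenia counts toward Table 5.

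The change concerns recording and tabulation only. Section 9.2.2 also links laboratory abnormalities above grade 2 to stopping of study drug, in a paragraph about non-hematologic values. The amendment should therefore make clear whether that sentence is meant to reach the newly recorded events.

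The counts are already collected every 2 weeks, so the cost is a protocol amendment, a clarifying sentence in 8.5, a few more event entries and one more table. The drawback is that some entries will reflect the disease or a co-medication rather than eltrombopag.
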